The research project will use a peer support model where long-term women prisoners will train the participants to use the MSC. Current peer support in prisons includes Listeners schemes, Insiders, Peer Advisors and Health Trainers (25). Established peer support schemes rely upon confidentiality in prisons and have been well received. A recent systematic review (26) found that 'peer support

services are acceptable within the prison environment and have a positive effect on recipients, practically and emotionally' and that 'consistent evidence from many, predominantly qualitative, studies, suggested that being a peer deliverer was also associated with positive effects'.

Aims and Objectives:

Primary Aim: To test feasibility and acceptability of medical skin camouflage for self-harm scarring in women prisoners.

Objectives: To test the feasibility of long term prisoners delivering the modified skin camouflage intervention in a local women's prison with a sample of prisoners with self-harm scarring. To test the feasibility of the women completing the baseline and outcome measures and a diary of their self-harm experiences during the research study. To evaluate acceptability of medical skin camouflage for women prisoners. To pilot collection of 3-month follow-up data from the women. To test the feasibility of collecting resource use data for the intervention using staff-completed proformas.

Research questions: Is it feasible for long term prisoners to deliver medical skin camouflage to fellow prisoners with self-harm scarring in the prison environment? What are the barriers to recruitment, participation, retention of women? Is skin camouflage acceptable to recipients and stakeholders in prison settings? What women, service and research-centred outcomes should be adopted in a future Randomised Control Trial?

Experimental Design and Methods:

Research Design: Randomised, wait-list control.

The feasibility pilot has four phases. Phase 1 and 2 were initially submitted and given ethical approval from North East – York REC REF: 16/NE/0030. Phase 1 and 2 have been completed and have informed the development of materials and conduct of phase 3 and 4. This application is for phase 3 and 4.

Phase 1: Focus Groups (completed)

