The sample size is 40 women prisoners overall. In the prison, there are ~40 active self-harming women prisoners per month (Nov 2013), of whom 25 have closed wounds, and 15-20 are likely to be eligible for camouflage per month. Our two recent consultations with stakeholders in the prison and the phase 1 focus group suggest interest in the intervention is high among women prisoners. 20 women prisoners will be randomised to receive the 6-week intervention; the other 20 women prisoners will be wait-list controls and receive the intervention after study completion. In the focus group with women we explored how they would feel about being randomly allocated to intervention or wait-list control and the women said they would not mind as they would still get to use the products after the research. As piloted in WORSHIP II, we shall censor women by release-date to reduce attrition, and try to follow the few women moved before the end of 6-weeks. If a woman has left prison before the three-month follow-up we will ask the prison to send the follow up letter to the women in the community. The women will have consented to this approach at the start of the research. Follow up in the community will involve completion of the questionnaires via distance methods e.g. email, post or telephone interviews. If a wait-list control woman leaves the prison

before the MSC is provided they will be instructed to contact the research team and will be posted their bespoke skin matched creams and powders.

Phase 4 Inclusion Criteria: Remand and sentenced women prisoners screened for date of release, with at least 6 weeks left on their sentence. The women will have passed the security vetting check which will be carried out by Safer Custody in association with prison officers to ensure that the researchers are safe during the project. The women will have self-harm scarring, with some closed wounds (to allow the MSC to be applied).

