Women will be given the cream and powder and will be able to keep these in their houses. Each woman has access to a safe and will have the choice of locking the products away if they wish. The research team and prison staff will make it clear to the women that the products should not be traded or shared with other women. Feedback from women prisoners in the phase 1 focus group suggested that they would not trade the make-up and therefore the likelihood of trading is deemed to be low. Members of the research team will meet with women on a weekly basis to do spot checks on the products and to collect the weekly diary. Prison staff advised that spot checks would be a good idea and are done for in possession medications so women are used to these procedures. If the

research team has any concerns about the products being shared or not used in the correct way they will discuss this issue with [name], the local collaborator.

Whilst using the products the women will be monitored, as usual, by [name] and his team in safer custody. They will ensure participant safety and if any participant needs to be referred to a care team or for another form of support within the prison this will be dealt with by [name]. Any events of self-harm which occur during the study period will be dealt with following ACCT procedures. Self-harm events will also be assessed to determine whether they are serious adverse events caused by participation in the research project. If so, the study has standard procedures which will be followed, as outlined in the standard operating procedures document. If a woman wishes to withdraw herself from the study she will inform [name] and, with the woman's permission, he will record the reason for withdrawal. Any women who withdraw from the study will be asked if they would like to meet with a member of the research team to talk about their participation in the project and why they wished to withdraw. It will be stressed that this is completely optional.

As requested by prison healthcare staff, the research team will explain that there is no guaranteed access to the medical skin camouflage products after the research. The research team will write follow-up GP letters for all of the women in the trial which will detail their involvement in the study and list the names of the products that they were prescribed. This will help women to access the products when they return to the community.

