All women in the treatment and control group will be skin matched at baseline. This will ensure that any wait list control participants who leave prison before the 3 month follow up will be able to be posted skin matched products by the research team on request.

Qualitative follow –up

(1) We shall undertake qualitative interviews examining acceptability of the intervention for participants, prison health and other prison/disciplinary staff. Approximately 20 participants who received the treatment will be invited by the team to evaluate their experience of the intervention and explore their views on treatment accessibility i.e. applying MSC, how long it stays on for, its perceived usefulness, effects on everyday life and potential impact on how women feel about their scarring, mood, self-esteem and self-confidence.

(2) Members of the research team will undertake a focus group with 6-10 prison health and other/disciplinary staff who have had direct contact with participants who received the treatment intervention. Their views will be explored in relation to the treatments' acceptability and perceived effects on participants' well-being, quality of life and everyday functioning.

(3) We shall undertake qualitative interviews examining acceptability of the training and being a practitioner in the prison. Six semi-structured interviews will be undertaken by the team to explore how acceptable the training was, how it was used with participants, mentoring/support from the research team and any benefits or difficulties working with participants.

(4) The Research Assistant will undertake four focus groups with women prisoners to explore what wellbeing means to them. This will help to inform the development of a 'wellbeing in prison' measure which could be used in future projects.

We have developed detailed interview schedules and topic guides to facilitate the qualitative elements of the study which were informed by the phase 1 focus groups.

Outcome measures:

1. Warwick-Edinburgh Mental Well-Being Scale (WEMWBS): a 14-item scale of mental well-being covering subjective well-being and psychological functioning, in which all items are worded positively and address aspects of positive mental health. The scale is scored by summing responses to each item answered on a 1 to 5 Likert scale. The minimum scale score is 14 and the maximum 70.

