8. Members of the prison staff will complete resource use proformas (based on the Secure Facilities Service use Schedule) for all participants and the research team will record including time spent by Changing Faces training the researchers, time spent by trained prisoners delivering the intervention, and quantities of MSC products used and prescribed. Descriptive analysis will inform future trial design.

9. Demographic and relevant personal history will be collected using a bespoke personal history questionnaire, previously used in a prison population in the WORSHIP projects.

As per HMPPS rules and regulations, no incentives or payments can be offered to participants whilst they are residing in the prison. However, the research team will provide an incentive for released women to complete follow-up outcome measures in the community. This will take the form of a £20 gift voucher, as well as reimbursement of travel expenses. This voucher will be given to compensate for their time and effort in coming to the appointment.

Analyses

(1) Feasibility and Acceptability: primarily qualitative (Phases I /4), but includes quantitative assessment of treatment attrition. Verbatim-transcription analysed using thematic content analysis.

(2) Quantitative data: Insufficient power for quantitative hypothesis testing means before and after treatment changes are descriptive including standard deviations and confidence intervals for outcome variables to inform sample size estimates for future RCT and assessment of feasibility of control group retention.

(3) Feasibility of delivering and acceptability and relevance to the prison population of EQ-5D-5L, SF-12 will be assessed through correlation between changes from baseline to follow-up of these and other piloted measures (WEMWBS, SOS-10, PANAS, BSSI, BDI, DSHI); and examination of completion rates. Descriptive analysis of HRQoL data will also be performed to inform the suitability of the measures for future clinical and economic evaluations of MSC in prison.

The resource use proformas will be assessed through time taken to complete the forms, completion rates, and ability to obtain included resource-use categories.

Survey

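### Participant acceptability interviews are limited to women who received the camouflage: non-starters fall outside them, early withdrawers have only an optional meeting not tied to the analysis, and no method is stated for decliners' reasons

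*Combined protocol and SAP*

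**What the plan says.** The primary aim, under Aims and Objectives, is "To test feasibility and acceptability of medical skin camouflage for self-harm scarring in women prisoners". Among the research questions is "What are the barriers to recruitment, participation, retention of women". Item (1) of Analyses describes how these are to be answered: "Feasibility and Acceptability: primarily qualitative (Phases I /4), but includes quantitative assessment of treatment attrition".

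For trial participants, the qualitative part is item (1) of Qualitative follow-up: "Approximately 20 participants who received the treatment will be invited by the team to evaluate their experience of the intervention". The topics listed there concern the product: applying it, how long it lasts, its usefulness, and its effect on daily life and on feelings about scars. Recruitment, random allocation, waiting and reasons for leaving are not among them. Item (2) adds a focus group with staff who had contact with treated women. Item (3) adds six interviews with the prisoners who deliver the intervention.

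The sample is set under Recruitment & Participants: "The sample size is 40 women prisoners overall", of whom "20 women prisoners will be randomised to receive the 6-week intervention" and "the other 20 women prisoners will be wait-list controls and receive the intervention after study completion".

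For withdrawal, Treatment Details provides for a reason to be recorded if the woman permits, and for an invitation to discuss her participation and her decision with the research team. On that meeting it adds: "It will be stressed that this is completely optional". The Phase 4 aims also list data on recruitment, participation, retention and causes of drop-out.

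**The concern.** The barriers question needs the views of women who did not get through the process as well as those who did. Eligibility for interview is conditional on having got through it. Under Treatment Details, receipt requires an appointment with a trained prisoner, a completed record form, a meeting with a nurse prescriber and a prescription. A woman can be lost after randomisation at any of these steps, and the protocol says elsewhere (Recruitment of long-term prisoners) that the prison cannot place transfer holds.

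Earlier still, Recruitment & Participants notes that expressing interest reveals to the prison that a woman self-harms. That is a plausible reason not to take part, and women already in the trial are poorly placed to report on it.

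At stake is the quality of evidence for a future trial. A count of non-starters or decliners shows that a problem exists. Only their reasons show whether it lies in the product, the supply route, disclosure, randomisation or prison movement.

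**Working it through.** No power or error-rate formula applies. The Analyses section itself says power is insufficient for hypothesis testing. The check sets each group of women against the planned sources, followed by simple counts.

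**Coverage by group**

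| Group | Item (1) interview | Other stated route | What remains open |
|---|---|---|---|
| Declines after the information sheet | No | Recruitment data | No method stated for reasons |
| Allocated to MSC, never starts, does not formally withdraw | No | Attrition count; diary, if kept | Reasons not sought in interview |
| Allocated to MSC, withdraws before receipt | No | Reason recorded with permission; optional meeting; cause of drop-out | Not tied to the thematic analysis |
| Received MSC, disliked it or stopped | Yes | Diary; withdrawal route if she leaves | Nothing material |
| Wait-list, still waiting | No | Diary; retention assessed descriptively; withdrawal route if she leaves | Views on allocation and waiting not specifically sought |
| Wait-list, treated after study completion | Not stated | As above | Eligibility for interview unclear |

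**Counts**

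Inputs from the protocol: 20 allocated to MSC, 20 wait-list, about 20 interviews.

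- Arms: 20 + 20 = 40, which agrees with the stated total.
- Interviews as a share of those randomised: 20/40 = 50%. The planned number equals the whole intervention arm.

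The protocol gives no non-receipt rate, so a range d is assumed. The arm can supply at most 20 × (1 − d) interviewees. If later-treated controls are not eligible, 40 − 20 × (1 − d) randomised women fall outside the interviews.

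| Assumed d | Recipients in the arm | Allocated to MSC but outside | All randomised outside |
|---|---|---|---|
| 0% | 20 | 0 | 20 |
| 10% | 18 | 2 | 22 |
| 20% | 16 | 4 | 24 |
| 30% | 14 | 6 | 26 |
| 40% | 12 | 8 | 28 |

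Two things follow. With any non-receipt, the target of about 20 can be reached only by counting wait-list women treated later, and the text does not say whether they count. And inviting all 20 allocated women takes 20 places, so it fits the planned total whatever d is.

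**The case against.** The strongest reply is that the plan does not rest on these interviews alone, and much of that reply stands.

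- A reader might infer that acceptability is explored only in recipients. It is not. Staff and practitioners are asked, and item (1) of Analyses also draws on the Phase 1 groups and on treatment attrition.
- A reader might infer that women who withdraw before treatment go unheard. Treatment Details offers the recorded reason and the meeting to any woman who withdraws, at any stage, and causes of drop-out are study data. The protocol is silent on whether the meetings are analysed; silence is not proof that they are excluded. The withdrawal procedure and the interview schedules exist as separate documents that are not included here.
- A reader might infer that the sample favours satisfied users. The criterion is receipt, not continued use, so a woman who tried MSC and gave it up is already eligible.
- Controls are not voiceless. Every participant keeps a weekly diary with room for free comments, and Phase 1 women were asked how they would feel about random allocation. A woman still waiting cannot describe her experience of using the product. The Phase 1 answer was, however, hypothetical and did not come from the trial's own controls.
- Reserving a fixed share of the interviews for controls would take places from women who used the product. That trade-off is debatable, and the point does not depend on it.

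What the reply does not reach is the non-starter who never formally withdraws, the missing method for decliners' reasons, and the missing link between the withdrawal meetings and the analysis.

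**Conclusion.** The concern holds in a limited form. As written, the participant interviews exclude women allocated to MSC who never start. Women who withdraw before receipt have a route, but not one connected to the thematic analysis. Decliners' reasons have no stated method of collection. The other sources cover the barriers question in part, so it would go too far to call it unanswerable.

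No size of bias should be claimed. It is tempting to argue that recipients could show 100% acceptability while the arm's true figure was 70% to 90%. That comparison supposes 2 to 6 of 20 women not treated (18/20 = 90%, 14/20 = 70%), with every one of them finding MSC unacceptable and every recipient finding it acceptable. The documents support none of these assumptions. Some non-receipt will reflect transfer or release rather than rejection, and the analysis is thematic, so no such percentage will be produced. The counts under the assumed non-receipt rates show only how many women would be outside the interviews, not what they would have said.

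**What to change.** 1. Reword item (1) of Qualitative follow-up to invite all women allocated to MSC, whether or not they received or continued it, within the planned total of about 20. Add a few topic-guide questions on barriers and on reasons for not starting or for leaving.
2. State whether wait-list women treated later are eligible. Use any unfilled places for controls' views on randomisation and waiting.
3. State in Analyses that, with consent, the recorded withdrawal reasons and the optional meetings enter the thematic analysis.
4. Keep an anonymous, optional one-line tally of reasons for declining after the information sheet. It should carry no identifying detail, so that it stays within the rule under Data Management that personal data are collected only with written consent.

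The cost is small topic-guide and consent-form edits, with no increase in the planned number of interviews. The downside is slightly fewer interview places for continuing users, mainly where later-treated controls would otherwise have filled them.

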Medical skin camouflage provides an essential resource for people with disfigurement from scarring, with the potential to restore self-esteem, confidence and therefore aid recovery (17-19). Medical skin camouflage uses BNF-listed preparations to disguise scars with the intention of normalising the appearance of the skin (20). The products include cover creams, liquids and powders that are waterproof, opaque and allow adherence to textured skin, including scarred areas. Each individual has a 'bespoke cream colour' and all the required products are available on NHS prescription at the discretion of the individual doctor (due to their status as borderline products). Only a handful of studies have evaluated the emotional/psychological benefits of medical skin camouflage. These have all been in dermatological diseases or burns scarring. They report significant psychological benefit, improved social and sexual relationships and the ability to secure employment (21-23). Despite this, few services offer medical skin camouflage for self-harm scarring (24). The current study has the added value that one of the co-applicants runs a new medical skin camouflage Service in partnership with Changing Faces – a registered charity, using volunteers to teach the medical skin camouflage techniques to people with mental health problems in the community. Preliminary findings from this innovative work indicate positive feedback from mental health service users with increased well-being, confidence and ability to partake in social activities.

In spite of the fact that self-harm is a considerable problem in prisons, there has been little focus on recovery or the use of medical skin camouflage in this setting. The project team has received feedback from individual medical skin camouflage practitioners who have used medical skin camouflage in HMP Holloway and HMP Eastwood Park. They report that the majority of women prisoners experience improved self-esteem and confidence as a result of using medical skin camouflage. However, no formal evaluation of outcomes related to recovery or improvement in

psychosocial functioning has been undertaken following use of medical skin camouflage in a prison environment and there are no published studies. In the phase 1 focus groups the women prisoners were enthusiastic about the products and said that they had the potential to improve their self-esteem, relationships with others and participating in activities such as going to the gym.

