The advertisement strategies were informed by consultation with prison staff and women prisoners in phase 1. Prison staff suggested that we present the research at monthly Queensland meetings which involve representatives from all of the houses. We will also go in the evening to Bollingwood, the open house outside of the main prison gate, to discuss the project with women who are on open house. We will distribute leaflets and posters at the Queensland meetings and these will then be displayed around the prison. We will also run a drop-in showcase and awareness session for ½ day each week which will take place in safer custody, with a member of safer custody staff present. This

will enable women to find out more about the trial and ask us questions about participation. Women will inform our local collaborator, the head of safer custody, [name], if they are interested in taking part in the research. The women who volunteer will be vetted by staff at the prison from Safer Custody and the Wings to ensure that they are safe and will not pose a risk to the researchers. Following vetting the women will be provided with an information sheet and offered the opportunity for the research team to visit and read through the sheet with them. Consent for the research will be agreed at least 24 hours after the information sheet has been read.

Prison staff informed us that we may identify some women who they do not know are self-harmers e.g. women who self-harm on their legs or torso. We will ensure in the meetings and showcase events that women know that by expressing their interest the prison will be aware of this and will know that they self-harm.

If a woman is excluded by the prison on the grounds of safety a member of the safer custody team will speak to them to inform them that they will be unable to participate in the research. The safer custody team are experienced in working with women who self-harm and supporting women in the prison. They will be able to deal with this sensitively and arrange the appropriate support for the woman if anything is required.

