With women's permission, we will also access information on key clinical characteristics from CNomis, SystemOne (the prison electronic medical records) and from ACCT documentation. These systems will be accessed by prison staff unless the researchers are given permission to access them. Consent to access the systems and extract information will be sought for all women. Information on relevant personal history including past psychiatric history, domestic violence, sexual abuse and parental neglect history will be collected using a bespoke demographic and personal history questionnaire which was used successfully in the WORSHIP projects. This information will be collected to check whether the two randomised groups have similar backgrounds.

During the 6-weeks skin camouflage intervention we will also ask each participant to complete a weekly diary. This idea was proposed by prison staff and women prisoners, some of who had completed a diary of self-harm thoughts and events in the past. The research team will collect the diary from the women at the end of the week. The diary will include any thoughts or acts of self-harm that have occurred during the week. It will also list any life events that have impacted on a women's self-harm. For the intervention group the diary will record their thoughts on the skin camouflage creams and powders. Women will also be able to note down any extra comments or thoughts from the week.

We will also pilot the collection of resource use data. A series of resource use pro-formas will be created for each woman. Prison staff will extract data from each of the prison systems. The pro-forma will be marked with the start date and end date (6 weeks apart) for the woman and resource use data will be extracted from Nomis, Officers logs, Business hub etc. Information on these systems will be redacted by prison staff before it can be passed on to the research team, e.g. to remove specific information about media-reported index offences. These systems will also be used to extract data on self-harm incidents which occurred during the 6-week intervention.

At post-intervention assessment. The following scales will be completed at 6 week's post-baseline and 3 months after the 6 weeks post-baseline assessment: DSHI, BSSI, BHS, BDI, EQ5D, SF12, WEMWBS, Rosenberg Self-esteem scale, DLQi, Zandarini PD Scale. Consent will be sought at baseline for women who have left prison before 3 months post-intervention to be followed up in the

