2. Becks Scale for Suicidal Ideation (BSSI): a 19-item instrument measuring intensity, duration and specificity of thoughts about committing suicide. The 19 items are rated on a three-point scale (0-2).
3. Becks Depression Inventory (BDI): a 21-item scale measuring symptoms of depression. Items are rated on a 4-point scale (0-3) with severity of self-reported depression: 0-9 minimal; 10-16 mild; 17-29 moderate and 30-63 severe.
4. Beck Hopelessness Scale (BHS): a 20-item self-report inventory designed to measure three major aspects of hopelessness: feelings about future, loss of motivation and expectations.
5. Deliberate Self-Harm Inventory (DSHI): a 17-item questionnaire giving history and frequency of self-harming behaviours.
6. Prison-adapted Dermatology Quality of Life Index (DLQi): a 7-item questionnaire adapted from a validated 10 item scale that has been used in over 40 different skin conditions in over 80 countries. The DLQi is the most frequently used instrument in studies of randomised controlled trials in dermatology.

7. Rosenberg Self-Esteem Scale: a 10-item Likert scale with items answered on a four-point scale – from strongly agree to strongly disagree. The scale measures self-esteem and has been used in prison research.

6. Incidence and frequency of self-harm will be collected from participant's prison records and the weekly diary.

7. We shall explore acceptability/relevance of two generic preference-based health-related quality of life (HRQoL) measures: The EQ-5D-5L covers five domains of health (mobility, self-care, usual activities, pain/discomfort, anxiety/depression). This new version was developed due to concerns over the lack of sensitivity to change of the original EQ-5D-3L, and consists of five severity levels for each domain (no, slight, moderate, severe, and extreme problems) rather than the original three levels (no, moderate, or extreme problems). Participants' responses are converted to a single index utility value based upon preference weights obtained from a UK general population sample.

SF-12 is a shortened version of the SF-35, consisting of twelve questions covering eight dimensions of health: physical functioning, role limitations - physical, bodily pain, general health, vitality, social functioning, role limitations - emotional, and mental health. A single index utility value is then obtained by applying published SF-6D preference weights.

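### Self-harm is taken from prison records, a diary and the DSHI with no planned comparison by arm, although the camouflage may itself change what the records capture

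*Combined protocol and SAP*

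**What the plan says.** The protocol measures self-harm in three ways.

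- **Records and diary.** The second item 6 of the Outcome measures list reads: "Incidence and frequency of self-harm will be collected from participant's prison records and the weekly diary". Under Phase 4, Outcome Measures, the record source is the set of prison systems used for resource data: "These systems will also be used to extract data on self-harm incidents which occurred during the 6-week intervention". On who does this: "Prison staff will extract data from each of the prison systems". No masking to arm is described. On the diary, the same section says "we will also ask each participant to complete a weekly diary". It covers acts as well as thoughts, in both arms.
- **DSHI.** This self-report inventory of history and frequency is completed at baseline, at 6 weeks, and 3 months after that.

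Three other statements bear on the records. In Recruitment & Participants, prison staff advised that "we may identify some women who they do not know are self-harmers e.g. women who self-harm on their legs or torso". The Justification section describes the products: "The products include cover creams, liquids and powders that are waterproof, opaque and allow adherence to textured skin, including scarred areas". The Phase 4 criteria require some closed wounds and exclude women who have only open ones.

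The Analyses section describes outcomes with standard deviations and confidence intervals. It correlates changes in the two quality-of-life measures with other scales, the DSHI among them. It judges the resource proformas on completion time, completion rate and whether the categories could be obtained. It does not set records against diary, and no section says which source defines the self-harm count or what happens when sources disagree.

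**The concern.** If staff learn of some self-harm by seeing it, a treatment that hides marked skin can lower the number of incidents recorded without lowering the number that occur. Only the MSC arm has the product during the 6-week count, because controls receive it afterwards. Safer custody staff attend the clinics, so the people around the record-keeping can know who is using it. The outcome's ascertainment may then depend on allocation.

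This matters even though the pilot tests no hypothesis. One research question asks which outcomes a future RCT should adopt, and the outcome summaries are meant to inform that trial's sample size. The protocol also expects less repeat self-harm and lower prison costs, and under-recording in the MSC arm would give the same signal. The pilot collects record and diary data on the same women over the same weeks, so it could look for the problem, but no such look is planned.

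**Working it through.** The only stated figure to reproduce is the sample size: 20 + 20 = 40, which checks. No event rate, recording rate or power is given, so the sizes below rest on assumed inputs.

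**Step 1. Is the mechanism possible, and in which direction?** The staff remark shows that awareness depends partly on body site and visibility. It is not a rule for how an incident enters the records. MSC goes on closed wounds, so a fresh cut cannot be covered until it closes. A wound that closes within the six weeks, or healed skin near a new one, can be covered in the MSC arm only. Against that, the research team checks products weekly with women who hold them, which may add scrutiny in that arm. A difference by arm is therefore possible, partial and uncertain in sign.

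**Step 2. Records alone, true rate ratio 1.** Let *v* be the share of recorded incidents found only by sight of the injury, and *c* the share of those hidden by cream. Neither is in the documents; both are assumed to lie between 0.10 and 0.50.

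Apparent ratio = 1 − *v* × *c*

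- *v* = *c* = 0.10: 1 − 0.01 = 0.99
- *v* = *c* = 0.25: 1 − 0.0625 = 0.94
- *v* = *c* = 0.50: 1 − 0.25 = 0.75

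**Step 3. An event counted if in records or diary.** Assume records capture 0.60 of events in controls and *v* × *c* = 0.25, so 0.60 × 0.75 = 0.45 in the MSC arm. Let the diary capture a share *q*, equal in both arms and independent of the records.

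Ratio = [1 − 0.55 × (1 − *q*)] / [1 − 0.40 × (1 − *q*)]

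- *q* = 0.50: 0.725 / 0.800 = 0.91
- *q* = 0.80: 0.890 / 0.920 = 0.97
- *q* = 0.95: 0.9725 / 0.980 = 0.99

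A combined count shrinks the distortion by an amount that depends on diary capture, but it also hides where the distortion arose.

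**Step 4. Could the pilot detect it?** With *m* mean events per woman and overdispersion φ (both assumed), SE of the log rate ratio = √[2φ / (20*m*)], and the 95% limits lie a factor exp(1.96 × SE) either side.

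- *m* = 2, φ = 1: SE = √(2/40) = 0.224, factor 1.55
- *m* = 2, φ = 5: SE = √(10/40) = 0.500, factor 2.66
- *m* = 5, φ = 1: SE = √(2/100) = 0.141, factor 1.32

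A ratio of 0.75 is a factor of 1/0.75 = 1.33. It is lost in the noise in the first two cases and borderline in the third. A between-arm difference in record counts could not be reliably attributed to detection, chance or benefit.

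**Step 5. What can the data show?** Full follow-up gives 20 × 6 = 120 woman-weeks per arm, each of which can be classified by record and diary. Weeks within a woman are correlated, so the information is less than 120 independent units. The table is still the most direct description of ascertainment by arm available from data already collected.

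**The case against.** The strongest reply is that self-report needs no one to see an injury. The diary is requested from both arms and the DSHI is also collected, so the plan does not rest on records alone. A reader might infer that the counts come from staff records that depend on visible injury. The documents do not support that: the sentence on incidence names the diary, and visibility is inferred from advice about recruitment. By volunteering, every woman makes her self-harm known to the prison. Monitoring by safer custody continues as usual, and the protocol's definition of self-harm includes ingestion, which cream cannot hide. All of this stands.

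A reader might also infer that the plan pools the sources into one outcome. It says only that data are collected from both, and is silent on combining them.

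On size, larger distortions can be calculated: hiding one third of otherwise recorded acts gives 0.67. Nothing in the documents supports an input of that kind, and the closed-wound limit argues against it.

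Finally, this is a descriptive feasibility study, so no efficacy conclusion is exposed. That is true, and it limits the seriousness of the point. It does not answer it, because choosing outcomes for the next trial is among the study's own questions.

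**Conclusion.** The point holds in a limited form. There are three self-harm sources, no statement of how they relate, and no comparison by arm, while the treatment may alter what one of them captures. Record-based ascertainment differing by arm is a credible risk, not an established bias.

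Under the assumed inputs the record ratio could lie between 0.99 and 0.75 with no true effect. Scrutiny from product checks could instead move it upwards. The real size and sign cannot be derived from the documents.

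It would be tempting to conclude that fewer recorded incidents in the MSC arm without fewer diary incidents proves concealment, or that the diary should be the lead measure. Neither follows. Chance, missing diaries and unblinded self-report could give the same pattern, 20 women per arm cannot separate these explanations, and which source to prefer is what the pilot should help to decide.

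**What to change.** Add to the Analyses section:

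1. Report prison-record, diary and DSHI self-harm separately by arm, and do not combine them into one count.
2. Tabulate record-diary agreement by arm per woman-week: both, diary only, record only, neither. Show diary completeness alongside, and keep weeks without a returned diary apart from weeks with a diary reporting no act.
3. State that a lower record count in the MSC arm without a lower diary count may reflect reduced detection, as well as chance, missing diaries or unblinded self-report, and will not be read as benefit on its own.
4. Use the table when choosing the self-harm outcome for the future RCT.

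The weekly table needs a date for each recorded incident, so the extraction form should keep that date through redaction. The cost is a few sentences and a little more descriptive analysis of data already being collected, with no added burden on participants. The downside is that agreement estimates will be imprecise at 20 per arm and should be presented as such.
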